**Effect of Vitamin D3 on Lung Function and Exercise
Tolerance in D3 Deficient COPD Patients**

ClinicalTrials.gov ID: NCT03781895

Document Date: December 23, 2018

PROJECT SUMMARY

Background: Chronic Obstructive Pulmonary Disease (COPD) is a major cause of morbidity and mortality throughout the world which is a preventable as well as treatable disease. It has some important extra pulmonary effects which may contribute to the magnitude of the severity of this disease. Standard therapeutic treatment alone does not optimize its remedy. Vitamin D₃ has been found to improve the physical efficiency of patients with various morbid disorders, including respiratory ailments. **Objectives:** To evaluate the effects of Vitamin D₃ on lung functions and exercise tolerance in patients with stable moderate COPD. **Methods:** For this, a prospective interventional randomized double blinded study will be carried out on 46 (eighty) vitamin D₃ deficient (serum 25 dihydroxycholecalciferol less than 30 ng/ml), male, stable (diagnosed patient, who has not experienced any acute exacerbation, hospitalizations, urgent care visits, or changes in routine medication within 4 weeks prior to study), moderate (post bronchodilator FEV₁/FVC < 0.70 of predicted value and FEV₁ = 50 to 79% of predicted value) COPD patients (age ≥ 40 years), who will be selected from the Out Patient Department (OPD) of the National Institute of Diseases of Chest and Hospital (NIDCH) and will be grouped as A (control) and B (study) groups, respectively. All the patients will be again designated as A0, A90 (with placebo) and B0, B90 (with D₃) for before and after 90 days of follow up. All the participants will be matched in terms of duration of COPD, history of smoking, occupation and socioeconomic status. Along with the standard pharmacological treatment of COPD, the patients of the 'Study group' will be prescribed for 80000 IU of oral vitamin D₃ per week for consecutive 3 months. Along with this, all patients both the groups will be advised to continue ad lib (according to their own choice) diet. At the very 1st day of the study, the lung functions will be assessed by measuring Forced vital capacity (FVC), Forced expiratory volume in one second (FEV₁), Forced expiratory ratio (FEV₁/FVC%), Peak expiratory flow rate (PEFR) and Forced mid expiratory flow of FVC (FEF_{25-75%}), with a portable digital spirometer. In addition, exercise tolerance will be assessed by change in 6 Minute Walk Distance (6MWD) in 6 Minute Walk Test (6MWT). Changes in peripheral capillary oxygen saturation (SpO₂) by Pulse Oximeter and degree of dyspnoea by Modified Borg Scale (MBS) will also be measured both before and after 6MWT to evaluate their change in both the groups. All these variables will be measured again after 90 days standard pharmacological treatment of COPD with D₃ intervention (B group) and also without D₃ intervention (A group). For statistical analysis, Chi-square test, independent sample 't' test between two groups, paired

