Investigator has applied for formal Clinical trials through www.Clinicaltrials.gov and was granted permission to go on with the trial (Annexure II) .On the first day of enrollment, the objectives, nature, purpose and potential risk of all the procedures used for the study will be explained in detail to each subject, with a cordial attitude giving emphasis on the benefits he might obtain from this study. He will be encouraged for voluntary participation and will be allowed to withdraw himself from the study even after participation, whenever he felt uneasy. If he agreed to be enrolled in the study, an informed written consent will be taken in a prescribed form (Annexure - IV). Detailed family history, medical history and thorough physical examination of each patient will be done and all the information will be recorded in a standard data sheet (Annexure - V). Then all the patients will be requested to attend the Department of Physiology at 9 am (about 1 and 1/2 hours after his breakfast) on the day of biochemical and spirometric examination.

On the examination day, 5 ml of venous blood will be collected and taken to the Hematology laboratory as soon as possible for the estimation of serum 25-hydroxycholecalceferol, serum glucose 2 hours after breakfast and serum creatinine. After that his height and weight will be measured and the spirometric lung function test will be done by using a portable spirometer. After getting all the biochemical and spirometric reports the final selection will be done, according to the inclusion and exclusion criteria.

Subsequently, all the eligible patients will be randomly assigned to either 'Control' or 'Study' groups and will be thoroughly informed about the objectives and detailed study procedure, once again. Then the patients will be examined for the baseline value of all the study variables in Day 1.

Again after 90 days the study variables will be collected from same 46 patients.

CONFOUNDING VARIABLES:

- Age: >40 years (Heideri 2015)
- Socioeconomic condition: Middle class (Martineau et al 2015)
- Smoking status: (Janssens et al 2010)
 - Current smoker = with history of active smoking
 - Ex-smoker = with history of 0 – 8 quit year
 - Duration = for >30 pack years
- BMI: 25 – 29.9 kg/meter-sq (Janssens et al 2010)
COPD patients at moderate stage according to GOLD criteria with > 4 years duration (Rees et al 2013)
- Stable COPD patients (Mehrparver et al 2010)
- Vitamin D₃ deficient: 30 ng/ml (Vitamin D council 2017)

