All the above mentioned variables will be similar ,statistically non significant in both the groups to ensure the minimization of their effects.

VITAMIN ADMINISTRATION :

Collection:

Vitamin D3

Ingredient

- Cholecalciferol (40,000IU)
- Microcrystalline Cellulose (58.1 gm)
- Butylated Hydroxy Toluene (0.2mg)
- Magnesium Stearate (3mg)
 - Gelatin Capsule Shell (1mg)

Dose : 80,000 IU/wk

Route : Oral

Placebo : Courtesy of Beximco Pharmaceuticals Limited Bangladesh

Ingredient : • Microcrystalline Cellulose (303.8gm) • Butylated Hydroxy Toluene (0.2mg)

- Magnesium Stearate (3mg)
- Gelatin Capsule Shell (1mg)

STUDY VARIABLES:

(1) Spirometric variables

- FVC (L) : Forced Vital Capacity
- FEV₁ (L) : Forced Expiratory Volume in 1st second
- FEV₁/FVC Ratio (%) : Forced Expiratory Ratio
- PEF_R (L/min) : Peak Expiratory Flow Rate
- FEF₂₅₋₇₅ (L/S) : Forced Expiratory Flow in the middle of FVC

(2) Oxygenation variables

- Resting SpO₂ (%) : Resting Peripheral Capillary Oxygen saturation

(3) Exercise tolerance variables

- 6MWD (meter) : Six Minute Walk Distance
- Level of Dyspnea : Modified Borg Scale

(4) Hematological variables

- 25(OH)D (ng/ml) : 25-hydroxycholecalciferol
- PTH (pmol/l) : Parathyroid hormone
- Ca²⁺ (mg/ml) : Ionic calcium
- PO₄³⁻ (mg/ml) : Ionic phosphate
- AP (U/L) : Alkaline Phosphatase

Subsequently a standard therapeutic treatment (according to GOLD guideline) (Annexure - VI) will be prescribed to all the selected stable moderate COPD patients. In addition, the patients of

the 'Study group' will be prescribed for 80000 IU of oral vitamin D₃ per week for consecutive 90 days . Along with this, all the patients of both the groups will be advised to continue ad lib (according to their own choice) diet.

Proper education will be given about drug , method of taking medication and medication plan. Afterwards, a good rapport will be built up to take time to time follow up over telephone and visiting patient's place . Schedule appointment , hotline and follow up will be maintained properly. They will be requested to attend the Department of Physiology again on the 90th day, to have the assessment of all the above-mentioned study variables

Any patient, who failed to follow the study procedure exactly during study period, will be dropped and a new one will be included to fulfill the desired total sample number. That's why extended sample should be taken to fulfill the total sample number.

Collection of blood sample (Afroza 2015):

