With all aseptic precaution, 5 ml of venous blood will be drawn from the antecubital vein by a disposable plastic syringe and was transferred immediately into a dry, clean test tube with a gentle push after removing needle, to avoid hemolysis. The test tube will be kept in slanting position till formation of clot. After centrifuging the clotted blood (at 3000 rpm for 10 minutes), the serum will be separated and taken into an Eppendorf tube and will be preserved in the refrigerator at -4°C in the laboratory. The serum level of all the intended variables will be done by an auto analyzer in the hematology lab of Department of Physiology, BSMMU.

Test procedure for spirometry (Afroza 2015):

- At first, the subject will be asked to take rest sitting on a chair and remain calm and quiet for 5 minutes.
- The detailed procedure will be explained to him to ensure his maximum cooperation.
- The switch of Spirometer will be on and windows will be open.
- Patients' information will be filled up and saved.

- The patient will be asked to hold a disposable paper mouthpiece (connected to spirometer) in his hand horizontally and to place it in between his two lips.
- To make good seal, he will also be asked to put the lips tightly around the outside of the mouthpiece.
- Then he will be asked to inhale first as deeply and as rapidly, as possible, which will be followed by a forceful expiration for the possible longest period into the mouthpiece.
- The readings of different variables will be recorded from the Spirometer monitor.
- Three (3) consecutive readings at 5 minutes interval for each parameter will be taken and the best value will be noted.

Test procedure for Pulse Oximetry (Afroza 2015):

- The patient will be asked to take rest and remain calm and quiet for 10 minutes (MacAllister et al 2007).
- The detailed procedure will be explained to him to ensure his maximum cooperation.
- Then his right index finger will be washed with alcohol and pulse oximeter sensor will be applied.
- The switch button will be on.
- The reading will be recorded from the display screen.
- Three (3) consecutive readings at 5 minutes interval will be taken and the best value will be noted.

Procedure for Six Minute Walk Test (6MWT) (Ahmed, Begum and Ali 2014):

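### On its natural reading, the best-of-three rule records the highest of three FEV₁/FVC ratios, which can never be below largest FEV₁ / largest FVC and pushes the ratio upward at entry and at both outcome visits

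*Combined protocol and SAP*

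**What the plan says.** Under 'Test procedure for spirometry', the patient is asked for a "forceful expiration for the possible longest period into the mouthpiece". Then "The readings of different variables will be recorded from the Spirometer monitor", and "Three (3) consecutive readings at 5 minutes interval for each parameter will be taken and the best value will be noted".

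The list of study variables has a separate entry, "FEV₁/FVC Ratio (%) : Forced Expiratory Ratio", beside FVC, FEV₁, PEFR and FEF25–75, and the data sheet gives the ratio its own line. Nothing says that the ratio is to be calculated from the recorded FEV₁ and FVC. No end-of-test, acceptability or repeatability criterion for a blow is given.

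The ratio has two uses:
- **Entry.** The Project Summary defines moderate COPD by "post bronchodilator FEV₁/FVC < 0.70 of predicted value" together with "FEV₁ = 50 to 79% of predicted value". The Study Procedure adds "After getting all the biochemical and spirometric reports the final selection will be done".
- **Outcome.** The spirometric variables are measured at day 0 and day 90. The Statistical Analysis section plans independent-sample t tests between groups and paired t tests within each group.

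**The concern.** For FEV₁, FVC and PEFR, the largest of three efforts is a sensible summary, because a poor effort can only lower the value. A ratio behaves differently. If the patient stops blowing early, FVC is cut while FEV₁ is hardly affected, and the ratio rises. Choosing the largest ratio therefore tends to favour a blow with a short FVC, and the recorded ratio need not equal recorded FEV₁ divided by recorded FVC.

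Two things are at stake. At entry, a patient whose ratio is truly just under the limit can be recorded at or above it and turned away. As an outcome, the ratio comes to depend on how well the patient blew at each visit as well as on lung function.

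**Working it through.** **Inputs from the documents.** Three blows per session, best value per parameter, FEV₁/FVC listed separately, ratio limit 0.70, 23 patients per group. The documents state no figure for the ratio's variability or bias, so there is none to reproduce first.

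**Step 1: direction (no assumptions).** Let j be the blow with the largest FEV₁. Then

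max(FEV₁/FVC) ≥ FEV₁ⱼ/FVCⱼ = max FEV₁ / FVCⱼ ≥ max FEV₁ / max FVC,

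because FVCⱼ cannot exceed max FVC. Illustration: blows of 1.80/3.00, 1.78/2.90 and 1.75/2.60 L have ratios 0.600, 0.614 and 0.673. The rule records 0.673; largest over largest is 1.80/3.00 = 0.600.

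**Step 2: size (assumed inputs).** Monte Carlo, three blows per patient, true ratio 0.62, normal within-session errors. 'Short blows' means that each blow has a one-in-five chance of an FVC 12% too low. Columns 2 to 4 take FEV₁ and FVC errors as independent; the last column gives the excess when they are correlated at 0.6.

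| CV FEV₁ / FVC | Highest ratio | Largest / largest | Excess | Excess, correlation 0.6 |
|---|---|---|---|---|
| 2% / 2% | 0.635 | 0.620 | 0.015 | 0.01 |
| 3% / 4% | 0.648 | 0.615 | 0.033 | 0.02 |
| 4% / 6% | 0.661 | 0.611 | 0.050 | 0.04 |
| 3% / 4%, short blows | 0.679 | 0.621 | 0.058 | 0.05 |

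A wider grid (true ratio 0.60, CVs of 2–6% for FEV₁ and 2–8% for FVC, 36 error structures) gave an excess of 0.006 to 0.084. No simulated patient violated Step 1.

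**Step 3: which blow supplies the highest ratio.** In the Step 2 model with correlation 0.6 and no short blows, it was the blow with the lowest FVC in 51–68% of patients. Over the wider grid the share was 23–90%. It is a tendency only.

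**Step 4: noise.** SD of the recorded ratio for a fixed true ratio, highest ratio against largest/largest:
- 3%/4% with short blows: 0.043 against 0.026, a variance ratio of (0.043/0.026)² ≈ 2.7.
- 3%/4%, no short blows, independent errors: 0.025 against 0.022.
- 3%/4%, no short blows, correlation 0.6: 0.016 against 0.016; at 2%/2% the order reverses slightly, 0.008 against 0.009.

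In the wider grid the highest ratio had the larger SD in 31 of 36 structures, including all 18 with incomplete blows.

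**Step 5: entry.** Every simulated patient is truly below 0.70. The percentages are those recorded at 0.70 or above.

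| Assumption | 2%/2% | 3%/4% | 3%/4%, short blows |
|---|---|---|---|
| Independent errors, true ratios uniform 0.55–0.70: highest ratio | 12% | 20% | 39% |
| Same, largest/largest | 4% | 5% | 7% |
| Correlation 0.6, uniform 0.55–0.70: highest ratio | 7% | 13–14% | 35% |
| Correlation 0.6, uniform 0.40–0.70: highest ratio | 4% | 7% | 17–18% |

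**Step 6: change over time.** At 3%/4% with independent errors, lowering the short-blow frequency from 20% to 10%, with lung function unchanged, moves the highest ratio by 0.014 and largest/largest by 0.003.

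**The case against.** The strongest reply is that the protocol says best, not highest. For a ratio, best could mean the value from the best manoeuvre, or whatever the spirometer reports by its own rule, which the documents do not describe. This stands as a limit on the claim: recording the highest ratio is the natural reading of a rule stated per parameter, not an explicit instruction. It does not remove the need for a change, because an undefined rule lets operators handle the ratio differently.

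A second reply is that the same rule applies in both randomised groups at both visits, so the average shift largely cancels between groups. That also stands. A reader might infer that the vitamin D₃ comparison is biased; the documents do not support this, since nothing suggests that blow quality differs by group in a design described as double blinded. Randomisation does not protect the within-group paired tests, where a change in blow quality between day 0 and day 90 can look like a gain or a loss.

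Third, the larger figures depend on assumptions. The one-in-five rate of short blows appears in no document, and patients are asked to exhale for as long as they can. Correlated errors or a wider spread of true ratios reduce the entry losses, as Step 5 shows. The Project Summary's wording of the limit, as a fraction of predicted, is itself unclear; the calculation takes it as a plain ratio of 0.70.

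Finally, the entry error acts in the cautious direction: it turns away borderline patients rather than admitting unobstructed ones. FEV₁/FVC is one of five spirometric variables, and FEV₁, FVC and PEFR are not affected.

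**Conclusion.** The point holds in a limited form. If the highest of three ratios is recorded, it can never be lower than largest FEV₁ / largest FVC; that part is algebra. The size is conditional: about 0.01–0.05 for within-session CVs of 2–4% (FEV₁) and 2–6% (FVC), and more with short blows. These CVs are assumptions.

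The practical costs are the wrongful exclusion of some patients near 0.70, and an outcome that responds to blow quality, chiefly in the paired within-group tests. Precision is clearly lost when some blows are incomplete.

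Two stronger readings should be resisted. One is that the recorded ratio always comes from the least complete blow; a high FEV₁ can produce it too. The other is that the ratio is always noisier; without short blows the SDs are similar and can reverse slightly. An effect on FEF25–75 is plausible, because that measure also depends on how complete FVC is, but it was not quantified.

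This should be corrected, but it does not threaten the trial's main comparison.

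**What to change.** Replace the best-of-three sentence in the spirometry procedure with wording such as: 'The largest FEV₁, the largest FVC and the largest PEFR of the three blows are recorded. FEV₁/FVC is calculated as largest FEV₁ / largest FVC. The same rule applies at screening, day 0 and day 90.'

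As a secondary suggestion, take FEF25–75 from the single blow with the largest FEV₁ + FVC. Written acceptability and repeatability criteria would address short blows at their source, but the change to the ratio does not depend on them.

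The cost is wording only. The same three blows are used, and the rule already keeps the largest FEV₁ and FVC, so the outcome ratio can be calculated from values recorded anyway. Exclusions already made on the highest ratio could not be undone this way.

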Alternate: Vitamin D₃ administration improves lung function and exercise tolerance in vitamin D₃ deficient stable COPD patients.

Objectives:

General Objective

To evaluate the effects of vitamin D₃ administration on lung functions and exercise tolerance in vitamin D₃ deficient male patients with stable COPD.

Specific Objectives

[figure not shown]
- To measure the FVC, FEV₁, FEV₁/FVC%, PEF and FEF_{25-75%} of vitamin D₃ insufficient male patients with stable moderate COPD, in order to assess their lung function status.
- To measure the SpO₂ at rest, in order to assess the basal oxygenation status in this group of patients.
- To determine level of dyspnea at rest, in order to assess the basal breathlessness level in the same group of patients
- To measure the 6MWD of all the patients, in order to assess their functional exercise capacity.
- To measure both the SpO₂ and level of dyspnea again after 6MWT, for the assessment of their exercise tolerance.
- To measure all these variables after 90 days standard pharmacological treatment with vitamin D₃ and also without vitamin D₃ in stable COPD patients.
- To compare the results of baseline and endline.

Methodology:

Consolidated Standard of Reporting Trials:

(Moher et al 2010)

CONSORT 2010 Flow Diagram

TYPE OF STUDY : Prospective interventional randomized double blinded study

PLACE OF STUDY : Department of Physiology, Bangabandhu Sheikh Mujib Medical University (BSMMU), Shahbagh, Dhaka

STUDY PERIOD : March 2017 to February 2018

STUDY POPULATION : Stable, moderate COPD patients with vitamin D₃ deficiency.

SAMPLE SIZE : 46

SAMPLING : Simple random sampling .

GROUPING OF THE SUBJECTS :

Group A : 23 D₃ deficient COPD patients without D₃ administration
(Control group)

A0 : On day 0

A90 : On day 90

Group B : 23 D₃ deficient COPD patients with D₃ administration
(Study group)

B0 : On day 0

B90 : On day 90

Subject Selection:

Inclusion Criteria

- Age: >40 years (Heideri 2015)
- Socioeconomic condition: Middle class (Martineau et al 2015)
- Smoking status: (Janssens et al 2010)
 - Current smoker = with history of active smoking
 - Ex-smoker = with history of 0 – 8 quit year
 - Duration = for >30 pack years
- BMI: 25 – 29.9 kg/meter-sq (Janssens et al 2010)
- COPD patients at moderate stage according to GOLD criteria with > 4 years duration (Rees et al 2013)
- Stable COPD patients (Mehrparver et al 2010)
- Vitamin D₃ deficient: 30 ng/ml (Vitamin D Council 2017)

Exclusion Criteria

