The 6MWT will be performed at indoors, along a long, flat, straight, enclosed corridor with a hard surface that is seldom traveled. The walking course will be 30 meter in length which will be marked every 3 meter. The turnaround points will be marked with a cone. A starting line, which marked

the beginning and end of each 60 meter lap, will be marked on the floor using brightly colored tape.

The subject will be asked to walk at his own maximal pace along the corridor from the end, covering as much ground as he can, during the allotted time, without running. He will be also advised to take rest if he will be too exhausted to continue the test. Standard phrases at regular intervals (every 60 seconds) will be used, like: “you are doing well,” “keep up the good work”. At the same time he will be also informed about the past time and how much has left before the test was completed.

If any of the subjects developed chest pain, intolerable dyspnoea, leg cramps, staggering, diaphoresis or pale appearance the test will be immediately stopped and the subject will be dropped. Again, when any subject will complete the total study procedure (according to the exact study design), he will be congratulated for good effort.

STATISTICAL ANALYSIS:

The results will be expressed as mean with standard deviation (mean \pm SD).

The data will be statistically analyzed by a computer with SPSS (Version 16.0) using Chi-square test,(to know the qualitative difference between the observed and expected result).Spirometric variables, oxygenation variables, exercise tolerance variables and hematological variables will be found between two groups of patients. If the variables are normally distributed , statistical analysis will be done by parametric statistical test. But if it is not normally distributed then it will be transformed into natural logarithm and again into anti logarithm, to make it normally distributed, then parametric statistical test will be done. Independent sample ‘t’ test between two groups, paired Student’s ‘t’ test within two specific measurements of different durations of each group will be done.

In the interpretation of results, ≤ 0.05 level of probability (p) will be accepted as significant.

PUBLICATION POLICY

- ❖ Scientific article to be published in a scientific journal.
- ❖ Presentation in scientific seminar or conference orally or through poster presentation.
- ❖ Website dissemination through internet version of JBSP.

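### The rule that drops a subject whose six-minute walk is stopped names no visit and leaves 'dropped' undefined, so at day 90 it can select patients on the exercise-tolerance outcome

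*Combined protocol and SAP*

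**What the plan says.** All references are to the combined protocol and SAP.

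- **Procedure for Six Minute Walk Test.** For any subject who develops "chest pain, intolerable dyspnoea, leg cramps, staggering, diaphoresis or pale appearance the test will be immediately stopped and the subject will be dropped". No visit is named. The next sentence turns to the other kind of subject: "when any subject will complete the total study procedure (according to the exact study design), he will be congratulated for good effort". Exhaustion alone is treated differently: "He will be also advised to take rest if he will be too exhausted to continue the test".
- **Visits.** The Project Summary says "All these variables will be measured again after 90 days standard pharmacological treatment of COPD", and the walk distance is among the variables listed there. The data sheet has before and after columns for day 0 and day 90.
- **Outcomes.** Under Study Variables, walk distance (6MWD) and Borg dyspnoea are the exercise-tolerance variables. The Specific Objectives add SpO2 and "level of dyspnea again after 6MWT, for the assessment of their exercise tolerance".
- **Other use of the word.** The follow-up text under Vitamin Administration says "Any patient, who failed to follow the study procedure exactly during study period, will be dropped and a new one will be included", with extra patients recruited to reach the planned total.
- **Study Procedure.** Baseline variables are measured after random assignment. Then: "Again after 90 days the study variables will be collected from same 46 patients".
- **Statistical Analysis.** An independent t test between groups, and a paired "test within two specific measurements of different durations of each group will be done". No analysis population and no handling of missing values is given.

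**The concern.** At day 90 the walk is an outcome assessment. A man stopped for intolerable dyspnoea has an extreme result on one exercise-tolerance variable and probably a short distance on the other. A rule that removes him removes a bad result because it is bad.

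If treatment changes who is stopped, the day-90 comparison is between groups selected on the outcome. A true benefit is understated if fewer treated than control patients are stopped, and overstated if more are. A harm is understated if more treated patients are stopped. If treatment does not affect stopping, the between-group comparison is not biased. The paired 6MWD gains within each arm are biased upward to the extent that stops go with short walks.

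The undefined term matters as well. Two competent analysts could build different data sets from this text, and a meaning chosen after unblinding would be a data-driven choice. With 23 per arm, each dropped patient is 1/23, or 4.3%, of his group.

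**Working it through.** **Reading the text.** The rule applies to any subject and the walk takes place at both visits, so day 90 is covered. Two readings of *dropped* remain.

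- *Removed from the study.* Favoured by the next sentence's contrast with a subject who completes the whole study, and by the follow-up text, where the word means removal with replacement. The day-90 walk outcomes are then lost selectively.
- *Test ended only.* The distance may or may not be kept; no visible text says.

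The Study Procedure's day-90 data on the same 46 fit the first reading only if 46 means final completers after replacement. A day-0 drop is also a post-randomisation exclusion, though before treatment has acted.

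**Inputs for the size.** From the documents: 23 + 23 = 46 patients. There is no stop rate, SD or effect to reproduce. Assumed: SD 90 m; true benefit d = 30 m; correlation ρ = 0.5–0.7 between 6MWD and a latent stopping sign; control stop rates 2%, 5%, 10%.

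**Formulas.** SE = 90 × √(2/23) = 26.54 m. If a fraction p is stopped, the retained mean rises by SD × ρ × λ(p), where λ(p) = φ(z_p)/(1 − p). Retained difference = d + SD × ρ × [λ(p_treated) − λ(p_control)].

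**Case 1: treatment lowers the stop rate.** The stopping sign shifts by ρd/SD (smaller loss) or d/SD (larger loss). Example with ρ = 0.5 and 5% in controls: the smaller shift is 0.5 × 30/90 = 0.167, which gives 3.5% stopped in the treated arm. λ is 0.1086 (control) and 0.0801 (treated), so the change is 90 × 0.5 × (0.0801 − 0.1086) = −1.28 m and 28.72 m is retained.

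| Control stop rate | Treated stop rate | Retained, ρ 0.5 (m) | Retained, ρ 0.7 (m) | Lost |
|---|---|---|---|---|
| 2% | 0.9–1.3% | 28.83–29.32 | 28.36–28.75 | 0.7–1.6 m (2–6%) |
| 5% | 2.4–3.5% | 27.71–28.72 | 26.80–27.60 | 1.3–3.2 m (4–11%) |
| 10% | 5.3–7.4% | 26.37–28.02 | 24.92–26.25 | 2.0–5.1 m (7–17%) |

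The loss is 0.03–0.19 SE. Upper bound, with stopping determined by distance alone (ρ = 1): 27.65, 25.43 and 22.74 m retained, a loss of at most 7.26/26.54 = 0.27 SE.

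**Case 2: treatment raises the stop rate, 5% to 10%.** λ(10%) − λ(5%) = 0.1950 − 0.1086 = 0.0864. The shift is 90 × 0.5 × 0.0864 = 3.9 m to 90 × 0.7 × 0.0864 = 5.4 m (0.15–0.21 SE) in favour of treatment. A true 30 m reads as 33.9–35.4 m, and no effect reads as 3.9–5.4 m.

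**Case 3: equal stop rates.** No between-group bias.

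**Paired change in controls.** Bias = (1 − r) × SD × ρ × λ(p), with assumed between-visit correlation r = 0.7–0.8: 0.4–0.9, 1.0–2.1 and 1.8–3.7 m upward at 2%, 5% and 10%. The paired SE, 90 × √(2(1 − r)/23), is 11.9–14.5 m, so this is 0.04–0.25 SE.

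**Chance that the rule is used at day 90.** 1 − (1 − p)^46 = 61%, 91% and 99% at 2%, 5% and 10%, with one rate for all 46. If the rule also screens at day 0 with the same cut-off and the stopping tendency correlates 0.7–0.8 between visits, these day-90 rates fall to about 1.2–1.4%, 2.7–3.2% and 4.9–5.9%, and the chances to about 43–48%, 72–78% and 90–94%.

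**The case against.** The strongest case is that this is a loose safety sentence with little numerical effect. The bias is a small fraction of the standard error and every input is assumed. Case 1 is conservative, and case 2 needs vitamin D3 to double the stop rate, which nothing in the documents suggests. Angina, heart failure, infarction and arrhythmia are exclusions, which removes some causes of the listed signs. Exhausted subjects may rest and stay in, and some triggers are only partly related to distance. The model also treats 6MWD as a full-walk normal variable, so the bias relative to a distance scored at the stop could be larger or smaller. All of this stands and limits the size. It does not answer the textual point that a patient can be excluded after randomisation because of his outcome.

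Three stronger readings are tempting, and the documents do not support them:

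- *The day-90 walk result is lost whatever 'dropped' means.* If only the test ends, nothing says that the partial distance is discarded, and the data sheet's distance line could hold it.
- *The rule contradicts the Study Procedure's count of 46.* The follow-up text plans extra recruitment and replacement, so 46 can mean final completers. The passages need reconciling, but they are not irreconcilable.
- *The data sheet has no place for an early stop.* Only part of the form is visible, and neither the pages before that part nor the flow diagram could be checked.

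A general rule keeping all randomised patients would cover most of this point. It would still not say how a stopped walk is scored.

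**Conclusion.** The concern holds as a defect of wording with a real but modest statistical consequence, and it should be fixed. Confidence is high that the rule names no visit, that *dropped* is undefined in the visible text and that the wording reaches day 90. It is much lower for the size, which rests wholly on the assumed SD, effect, correlations and stop rates. Within those ranges the between-group bias stays at or below about 0.2 SE, in a direction that depends on how treatment affects stopping. The rule is likely to be used at least once unless stops are very rare, and less likely if day 0 has already removed stop-prone patients. The case for change is that an undefined exclusion tied to an outcome can be removed at almost no cost.

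**What to change.** Leave the safety stop and its criteria as they are, and change only the data handling.

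1. **Six-minute walk procedure, day-90 walk.** Replace the clause that drops the subject with: *the distance walked up to the stop is recorded as the 6MWD; Borg score and SpO2 at the stop are recorded and flagged as taken at an early stop; the subject's day-90 data are kept and analysed in his assigned group.*
2. **Follow-up text under Vitamin Administration.** Add: *a stopped day-90 walk is not a failure to follow the study procedure and does not lead to replacement.*
3. **Statistical Analysis.** Add: *stopped day-90 walks are included in the between-group and paired tests; their number and reasons are reported by arm.*
4. **Data sheet.** Add one line, if none exists: stopped early (yes/no), time, reason.
5. **Day 0.** Reconcile the Study Procedure, the follow-up text and the walk procedure on what *dropped* means for a walk stopped at baseline, and report such drops by arm. Whether that patient continues is for the sponsor to decide.

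Settle this before unblinded data are seen. The cost is a few sentences, at most one data-sheet line and one table row, with no new measurement.

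There are two downsides. Borg and SpO2 at an early stop are not fully comparable with values after six minutes, hence the flag. One very short walk also adds noise: an assumed 200–300 m below the mean of the rest of the arm moves that arm's mean by 200/23 to 300/23, or 9–13 m, and raises the SE from 26.5 to about 27.6–29.3 m. That exceeds the bias being repaired, but it is noise and not selection.
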